2. N/A

V. Data Analysis and Reporting

- A. Statistical and Data Analysis:** Data will be checked for errors, inconsistencies, and missing values. Descriptive statistics (e.g., mean and standard deviation for continuous variables and number and percent for categorical variables) will be presented for all demographic variables, predictors of interest, and outcomes. Chi-square and 2-sample t-tests will be used to compare the outcomes among demographic groups and between different treatments.
- B. Outcome:** Blood pressure rates
- i. Hypertensive-range BP is defined as SBP ≥ 140 and/or DBP ≥ 90 mm Hg; severe-range BP is SBP ≥ 160 and/or DBP ≥ 110 mm Hg.
 - ii. Severe-range hypertension (obstetric emergency threshold): SBP ≥ 160 or DBP ≥ 110
- C. Study results to participants:** N/A
- D. Publication Plan:** Three publications will be done: Implementation of the study, analysis of study results, and health behaviors of participants.
- E. Bibliography / References / Literature Cited**

2. ACOG. Gestational Hypertension and Preeclampsia. *Obstetrics & Gynecology* 2019;133:1-25.
4. Sibai B. Diagnosis and Management of Gestational Hypertension and Preeclampsia. *Obstetrics and Gynecology (New York 1953)* 2003;102:181-192.
5. Backes CH. Maternal preeclampsia and neonatal outcomes. *Journal of pregnancy* 2011;2011:1-7.
8. Raymond D. A critical review of early-onset and late-onset preeclampsia. *Obstetrical & gynecological survey* 2011;66:497-506.

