Official Study Title

Improving Prenatal Care to Reduce Early Onset Preeclampsia in Low-Income Black Women in Kansas

ClinicalTrials.gov Identifier

NCT Number: *Pending registration at ClinicalTrials.gov*

Principal Investigator

[name], PhD

University of Kansas Medical Center (KUMC)

Study Sponsor

National Institutes of Health (NIH)

IRB Protocol Number

STUDY00160319

Version Date of This Protocol Document

February 9, 2026

Site Name: University of Kansas Medical Center

Kansas City, Kansas

University of Kansas Medical Center
RESEARCH PROTOCOL INVOLVING HUMAN SUBJECTS
TEMPLATE WITH GUIDANCE

Version date: 02.09.2026

Principal Investigator: [name]

Study Title: *Improving Prenatal Care to Reduce Early Onset Preeclampsia in Low-Income Black Women in Kansas*

[name], [name], [name], [name], [name]

1. Protocol Synopsis

Study Design

Prospective, two-arm randomized controlled trial; parallel assignment; open-label (behavioral/telehealth intervention).

Randomization: 2:1 allocation using REDCap with variable block sizes.

Framework: Practical, Robust Implementation, and Sustainability Model (PRISM) to guide implementation, adoption, effectiveness, maintenance, and pragmatism evaluation.

Population

Pregnant participants, age ≥ 18 years.

English or Spanish speaking.

Less than 13 weeks gestation at enrollment.

Moderate or high risk for preeclampsia per USPSTF criteria.

Intervention (Arm 2)

Centering HER (HGPC-T): routine prenatal care plus 7 doula-led virtual group sessions (90 minutes each) with OB/GYN fellow oversight.

Participants receive Bluetooth BP cuff and (if applicable) Apple Watch; self-monitor and self-report blood pressure and weight; complete surveys and medication log (if applicable).

Comparator (Arm 1)

Usual doula prenatal care and routine prenatal care visits with OB/GYN; completes study surveys.

Primary/Key Outcomes (as stated in source protocol)

Blood pressure rates; hypertension monitoring and aspirin compliance (# of women monitoring BP and aspirin compliance).

Feasibility, acceptability, and contextual factors required for implementation.

Duration

Enrollment at <13 weeks gestation through postpartum survey completion (baseline, antepartum, and postpartum surveys).

Data Sources

REDCap surveys (baseline, antepartum, postpartum).

Self-reported BP/weight (device-supported); medication log (if applicable).

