1. Inclusion criteria: English or Spanish speaking, <13 weeks gestations, >18 years old, moderate or high risk for preeclampsia according to the United States Preventative Services Task Force (USPSTF): **High Risk:** History of preeclampsia (especially with an adverse outcome); Multifetal gestation; Chronic hypertension; Pregestational type 1 or type 2 diabetes; Kidney disease; Autoimmune disease (e.g., systemic lupus erythematosus, antiphospholipid syndrome) **Moderate Risk:** Nulliparity (first pregnancy); Obesity (pre-pregnancy BMI > 30); Family history of preeclampsia (mother or sister); Black persons (due to social, not biological, factors); Lower income; Age ≥ 35 years; Personal history factors (e.g., low birth weight or small for gestational age, previous adverse pregnancy outcome, >10-year pregnancy interval); In vitro conception (IVF)
2. Exclusion criteria: <18 and not receiving prenatal care or eligible for doula care
3. Withdrawal/Termination criteria: N/A

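### The 140/90 outcome is not tied to baseline status although chronic hypertension is an inclusion factor, so the unadjusted comparison mixes pre-existing with pregnancy-related hypertension

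*Protocol*

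**What the plan says.** Section V.B names the outcome "Blood pressure rates" and sets a threshold: "Hypertensive-range BP is defined as SBP ≥ 140 and/or DBP ≥ 90 mm Hg". A severe range, at 160/110, follows. The definition contains no new-onset condition, no reference to BP at entry, no time window and no rule for turning readings into a result per woman. The synopsis lists the outcome in the same form: "Blood pressure rates; hypertension monitoring and aspirin compliance".

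The high-risk inclusion factors in section II.D.1 include "Chronic hypertension; Pregestational type 1 or type 2 diabetes; Kidney disease". The exclusion line mentions no blood pressure: "Exclusion criteria: <18 and not receiving prenatal care or eligible for doula care". The synopsis sets entry early in pregnancy: "Less than 13 weeks gestation at enrollment".

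Section V.A, repeating section II.C, gives the analysis: "Chi-square and 2-sample t-tests will be used to compare the outcomes among demographic groups and between different treatments". No baseline covariate or stratum is stated. Section II.B describes 2:1 randomisation of 72 women in variable blocks and names no stratification factor. Aims 2 and 3 in section I.A concern reducing preeclampsia. The central hypothesis there covers both monitoring of chronic hypertension and reduction of early-onset preeclampsia.

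**The concern.** A woman enrolled before 13 weeks with chronic hypertension may already be at or above 140/90 before the first group session. For her, crossing the threshold later says something about control of an existing condition. For a woman who enters with normal pressure, it says something about new disease. The outcome as written does not distinguish the two, and the named test pools them.

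Two things are at stake. The first is interpretation: a difference, or the lack of one, cannot be read as an effect on pregnancy-related hypertension. The second is precision: with about 24 controls and no stratification, a few more women with chronic hypertension in one arm can move the result noticeably. An adjustment elsewhere could reduce the noise, but it would not change what the outcome counts.

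**Working it through.** **Plan's own figure.** There is none to reproduce. Section II.C states that this is a pilot without a power calculation.

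**Inputs from the protocol.** 72 women at 2:1, so 72 × 2/3 = 48 intervention and 72 × 1/3 = 24 control (section II.B). The timeline table's 36 per group conflicts with this. That is a separate point and does not change the directions below.

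**Assumptions (none is in the documents).**
- f = share of women in hypertensive range at entry: 10%, 20% or 30%.
- p = risk in the other women: 40% control, 15% intervention.
- q = risk in women hypertensive at entry. Case A, no response: 100% in both arms. Case B, response: 90% control, 60% intervention.

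**Step 1: risk difference.** Arm rate = f·q + (1−f)·p, so RD = f·(q_C − q_I) + (1−f)·(p_C − p_I).
- Case A, f = 20%: control 0.20 + 0.80 × 0.40 = 0.52; intervention 0.20 + 0.80 × 0.15 = 0.32; RD = 0.20 instead of 0.25. In this case the difference shrinks by exactly the factor (1−f).
- Case B, f = 20%: control 0.18 + 0.32 = 0.50; intervention 0.12 + 0.12 = 0.24; RD = 0.26, slightly above 0.25.

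**Step 2: chance imbalance.** SD of the between-arm difference in f = √[f(1−f)(1/48 + 1/24)]. At f = 20%: √(0.16 × 0.0625) = 0.10. In case A, an imbalance of δ moves the observed difference by δ × (1−p). For δ = 10 points this is 10 × 0.60 = 6.0 points at p = 40% and 10 × 0.85 = 8.5 points at p = 15%.

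**Step 3: power.** 200,000 simulated trials per setting, 48:24, z > 1.96 in favour of the intervention. The pooled two-proportion z was used for the unadjusted tests and the Mantel-Haenszel statistic for the stratified one.

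| f | Case | RD, all women | Unadjusted, all women | Unadjusted, only women not hypertensive at entry | Mantel-Haenszel, all women |
|---|---|---|---|---|---|
| 10% | A | 0.225 | 51% | 61% | 61% |
| 20% | A | 0.200 | 38% | 57% | 56% |
| 30% | A | 0.175 | 30% | 51% | 51% |
| 10% | B | 0.255 | 64% | 61% | 66% |
| 20% | B | 0.260 | 61% | 57% | 68% |
| 30% | B | 0.265 | 60% | 51% | 69% |

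With 30% versus 15% in the other women, case A and f = 20%, the three powers are 18%, 28% and 28%.

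**Step 4: type I error.** With equal arms (30% in the other women, 90% or 100% in women hypertensive at entry), the two-sided rejection rate was about 5% for the stratified test and 5.2% to 5.5% for the unadjusted one.

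**Limit of the calculation.** The simulated stratum is hypertension at entry. Stratifying on chronic-hypertension history instead separates the groups less sharply where that hypertension is controlled.

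**The case against.** The strongest objection is that women with chronic hypertension are part of the target. The central hypothesis names monitoring of chronic hypertension, and the medication log in Appendix E tracks antihypertensive adherence. Better control in these women is a legitimate effect, and case B shows that it can enlarge the absolute difference. This stands. A reader might infer that the threshold dilutes any effect and that these women should be removed. The documents do not support that: dilution requires that they exceed the threshold regardless of arm, and in case B restricting the outcome lowers power from 61% to 57% at f = 20%.

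Second, a reader might infer that prevalent cases are counted as events before the first session. Section V.B does not say so. It gives no ever/never rule, and a share of readings, a late-pregnancy value or mean BP compared by t-test would behave differently. Women with controlled hypertension may not meet the threshold at all. This also stands, but the missing link to baseline remains under any binary version.

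Third, randomisation balances the groups in expectation, so there is no systematic bias, and the trial makes no power claim. Both are correct. Section V.A nevertheless plans a between-arm comparison and section V.D a publication of the results.

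Finally, a statistical analysis plan that is not shown may contain an adjustment. That could improve precision. The outcome definition and the named test, however, are fixed in the protocol.

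**Conclusion.** The point holds as one of interpretability, sensitivity and chance imbalance. The 140/90 outcome cannot by itself separate pre-existing from pregnancy-related hypertension, although the protocol admits both groups and asks about preeclampsia.

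The size depends on assumed rates. At 20% prevalence the SD of chance imbalance is about 10 points. The loss from 25 to 20 points, and power of 38% against 57%, apply only if women hypertensive at entry exceed the threshold in both arms whatever the treatment. If they respond, the absolute difference does not shrink. In every effect setting tabulated, the stratified analysis of all women had higher power than the unadjusted one, without inflating type I error. The case for stratifying therefore does not depend on which assumption is true.

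**What to change.** In sections V.A and V.B (and the matching text in II.C):

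1. Make the between-arm comparison of hypertensive-range BP a Mantel-Haenszel estimate stratified by chronic-hypertension status at entry, and keep all randomised women in it.
2. Count only readings taken after randomisation.
3. Report the two strata separately. Name new-onset hypertensive-range BP in women without chronic hypertension as the result that speaks to prevention.

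The cost is a change of wording and slightly more analysis. Chronic hypertension is already an eligibility factor, so the stratifier should be available from screening. A baseline BP reading is not expressly scheduled, so stratify on chronic-hypertension history unless the EHR abstraction supplies an entry reading. The strata will be small in a 72-woman pilot, and the stratum results should be presented as estimates with intervals.

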APPENDIX I: VULNERABLE POPULATIONS

- I. Pregnant women ages 18-35, pregnant women data will be protected on the p:drive for surveys, no medical data will be provided during group discussions, participants will be asked to use their first names during group or a name they would like to use.
- II. Cognitively or decisionally impaired individuals: N/A
- III. Children: N/A
- IV. Pregnant women: Yes
- V. Prisoners: N/A

VI. Students and/or Employees:

- A. N/A
- B. N/A
- C. N/A

17. Attachments List (IRB Submission Packet)

Attachment 1: Informed Consent Form template (Appendix A).
Attachment 2: Recruitment materials and scripts (Appendix B).
Attachment 3: Virtual Group Confidentiality Agreement (Appendix C).
Attachment 4: Safety workflows (Appendix D): Severe BP escalation; Acute distress/suicidality response (as applicable).
Attachment 5: Measures/Instrument packet (Appendix E): baseline/antepartum/postpartum surveys; BP/weight log; medication log (if applicable).
Attachment 6: Schedule of Events and Timeline tables (Sections 4.1 and 5).
Attachment 7: Data and Safety Monitoring Plan details (Section 10).

Appendix D. Safety Workflows (SOP)

D1. Severe Blood Pressure Escalation Workflow

Trigger: Any home blood pressure reading in the severe range (e.g., systolic ≥ 160 and/or diastolic ≥ 110), or symptoms suggestive of hypertensive emergency (e.g., severe headache, vision changes, chest pain, shortness of breath, RUQ pain).

If severe BP or severe symptoms: instruct participant to seek emergency care immediately (call 911 or go to the nearest emergency department).

If elevated but not severe: instruct participant to repeat measurement after 5–10 minutes of rest and contact their prenatal care team the same day for guidance.

Document the report (date/time, reading, symptoms, actions taken) in REDCap safety log.

Notify PI or designee within 24 hours of any severe-range report.

Appendix E. Measures and Instruments Packet (Inventory)

Instrument / Data Source	Purpose	Timepoints	Notes / Storage
Baseline Survey (REDCap)	Demographics, baseline health behaviors/knowledge, baseline outcomes per study measures table	Baseline (<13 weeks)	Store in REDCap; authorized versions in regulatory binder
Antepartum Survey (REDCap)	Follow-up outcomes and process measures	Late pregnancy / last prenatal visit before delivery	Store in REDCap
Postpartum Survey (REDCap)	Postpartum outcomes and acceptability	Postpartum	Store in REDCap
Home BP and Weight Log (device-supported)	Daily/regular monitoring	Throughout participation	Self-report; Bluetooth cuff/Apple Watch (if applicable)
Medication Log (if applicable)	Aspirin and/or antihypertensive adherence tracking	Throughout participation	Self-report; may be verified by doula if built into workflow
EHR Abstraction	Clinical outcomes including blood pressure, prenatal care utilization, delivery outcomes (as defined)	Ongoing / postpartum	Minimum necessary data; stored on p:protecteddata drive
